Study Title “The Efficacy Of Intravenous Immunoglobulin Therapy
In Treatment Induced Neuropathy Of Diabetes”

NCT number: NCT02915263

Version 2.0

Document Date: Revised 11/10/2016 (Original 9/10/2016)

Protocol:

This study will be a double-blind, placebo-controlled pilot study of the effects of immune globulin (IVIG) on treatment induced neuropathy in diabetes. The goal of this pilot study is to obtain preliminary data on the magnitude of the treatment effect of IVIG on the neuropathic pain and neuropathy severity associated with TIND. The preliminary data will be used to power a larger treatment trial, and to aid our understanding of the mitigating factors in the treatment response.

The study will include a total 20 individuals. Subjects will be randomized equally to treatment or placebo. Treatment will consist of IVIG administered at 2 grams/kg divided over 2-4 days, with a follow up treatment 3 weeks (+/-3 days) later of IVIG 1gram/kg administered over 1 day.

Subjects: All individuals participating in the study will be recruited from Joslin Diabetes Center or Beth Israel Deaconess Medical Center from the clinical practice of [name]. Recruited subjects will review and sign the informed consent, undergo screening for eligibility:

Inclusion Criteria:

- Individuals with a diagnosis of diabetes and treatment induced neuropathy (defined by the onset of neuropathic pain within 8 weeks of a change in HbA1C exceeding 3 points over 3 months).
- Ages 18-60.
-

Exclusion Criteria:

- No other known cause of neuropathy (chemotherapy, toxins, other medical disorder).
- Anticoagulation with warfarin, aspirin & Plavix together, or other anticoagulant that would place subjects at undue risk of bleeding from a skin biopsy. Aspirin or Plavix alone are not an exclusion criteria.
- Evidence of severe vascular disease (history of ulceration, poor wound healing, vascular claudication)
- Clinically active coronary artery or cerebrovascular disease
- History of allergic reaction to local anesthesia for skin biopsies or history of scarring or keloid formation.
- History of reaction to blood products or immune globulin.

Screening Visit (Visit 1): Protocol Procedures- After signing an informed consent subjects will undergo the following:

- 1) Undergo a general physical examination, Pain VAS scores, pain questionnaires and SF-36.
- 2) Have a quantified neurological (neuropathy) examination using the Utah Early Neuropathy Score (UENS)(Singleton *et al.*, 2008).

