- 3) Undergo autonomic testing (heart rate variability to paced breathing)(Gibbons and Freeman, 2004). Heart rate variability is measured over the course of 6 deep inspirations with the peak maximal average heart rates subtracted from the lowest heart rates during each breathing cycle.
- 4) Undergo a 3mm punch skin biopsy at the distal leg to investigate small sensory and autonomic innervation using standard methodology (Gibbons *et al.*, 2009, Wang and Gibbons, 2013). Outcome measures will include intra-epidermal nerve fiber density (IENFD).
- 5) Quantitative review of additional clinical outpatient data (renal function, retinopathy screening, laboratory studies).

(Visit 2) Outpatient treatment 1: IVIG 2 grams/kg over 2-5 days (to be administered within 28 days of screening visit).

SF-36 questionnaire.

Placebo would include administration of 0.1% albumin per day over 2-5 days.

(Visit 3) Outpatient treatment 2: IVIG 1 gram/kg over 1 day (to be administered 21±3 days after completion of initial treatment).

SF-36 Questionnaire.

Placebo would include administration of 0.1% albumin per day over 1 day.

Visit 4: Follow up evaluation at BIDMC 28 +/- 3 days after 2nd IVIG treatment where they will undergo the following:

- 1) Undergo a general physical examination. Pain VAS scores, pain questionnaires and SF-36.
- 2) Have a quantified neurological (neuropathy) examination using the Utah Early Neuropathy Score (UENS)(Singleton *et al.*, 2008).
- 3) Undergo autonomic testing (heart rate variability to paced breathing)(Gibbons and Freeman, 2004). Heart rate variability is measured over the course of 6 deep inspirations with the peak maximal average heart rates subtracted from the lowest heart rates during each breathing cycle.
- 4) Undergo a 3mm punch skin biopsy at the distal leg to investigate small sensory and autonomic innervation using standard methodology (Gibbons *et al.*, 2009, Wang and Gibbons, 2013). Outcome measures will include intra-epidermal nerve fiber density (IENFD).
- 5) Quantitative review of additional clinical outpatient data (renal function, retinopathy screening, laboratory studies).

DOSING REGIMEN (Describe the subject or animal dosing)

(Visit 2) Outpatient treatment 1: IVIG 2 grams/kg over 2-5 days (to be administered within 28 days of screening visit).

Placebo would include administration of 0.1% albumin per day over 2-5 days.

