(Visit 3) Outpatient treatment 2: IVIG 1 gram/kg over 1 day (to be administered 21±3 days after completion of initial treatment).

Placebo would include administration of 0.1% albumin per day over 1 day.

Selection of Placebo: The inclusion of placebo is critically important in a pilot study of this type in order to understand the potential treatment effects of IVIG on disease. Low dose albumin has been selected as the choice of placebo based on standard dosing from several other clinical trials of IVIG in different forms of neuropathy.

OBJECTIVES (Succinctly describe the major objectives for the overall proposed project)

To develop a therapeutic intervention for treatment induced neuropathy in diabetes. The primary endpoint will be to improve the pain associated with TIND, as well as improve nerve fiber structure (measured by biopsy analysis of IENFD) and by improvement in nerve fiber function.

Finally, we will improve our understanding of the potential mechanisms underlying this disorder, and define a potential plasma biomarker (elevated cytokines and inflammatory markers) that could identify patients that would respond to the treatment.

Primary endpoint:

The change in neuropathic pain severity and distribution between treatment and placebo groups between visit 1 and visit 2.

We expect that individuals with TIND treated with IVIG will have a >50% reduction in neuropathic pain and >30% reduction in the distribution of neuropathic pain 6 weeks after treatment. We expect that placebo that will have <20% reduction in neuropathic pain and no change in the distribution of neuropathic pain 6 weeks after treatment.

Secondary Outcomes:

The difference in quantified neurologic examination scores, biopsy scores and autonomic function between treatment and placebo groups at 6 weeks and 12 weeks.

We expect that individuals with TIND treated with IVIG will have improvements in quantified neurologic examination scores, autonomic function testing and nerve fiber density at follow up visits 4 and 5 compared to their initial visit. We expect that placebo treated individuals will have either no change or worsening of quantified neurologic examination scores, autonomic function testing and nerve fiber density at follow up visits 4 and 5 compared to their initial visit.

Exploratory Outcomes:

Exploratory outcome measures will include the effects of cytokine on neuropathic pain, small fiber neuropathy and autonomic neuropathy (heart rate variability).

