Statistical Analysis Plan

Power calculations:

This pilot study is being conducted in order to obtain adequate preliminary data for a larger clinical trial, but is powered to answer the primary endpoint analysis. Secondary endpoints and exploratory endpoints are not included in the power analysis

Group	Change in pain score	Change in IENFD
Placebo	2+/-2	0.5+/-1
IVIG	5+/-3	3+/-1.9

Number of pairs needed for 80% power to detect change.	10	7
---	-----------	----------

Change in pain score calculation: We are planning a study of a continuous response variable from matched pairs of study subjects. Prior data indicate that the difference in the pain response of matched pairs is normally distributed with standard deviation 3. If the true difference in the mean response of matched pairs is 3, we will need to study 10 pairs of subjects to be able to reject the null hypothesis that this response difference is zero with probability (power) 0.8. The Type I error probability associated with this test of this null hypothesis is 0.05.

Change in IENFD score calculation: We are planning a study of a continuous response variable from matched pairs of study subjects. Prior data indicate that the difference in the response of matched pairs is normally distributed with standard deviation 1.9. If the true difference in the mean response of matched pairs is 2.5, we will need to study 7 pairs of subjects to be able to reject the null hypothesis that this response difference is zero with probability (power) 0.8. The Type I error probability associated with this test of this null hypothesis is 0.05.

Based on our preliminary data from the 4 subjects treated with IVIG, and the 104 untreated subjects with TIND, and the power analysis listed in Table 3, we calculate that 10 subjects in each of the treatment and placebo treated arms will provide >80% power with a 2 sided alpha of 0.05 to detect a difference between placebo and active treatment groups.

A total of 20 subjects will be included in this study:

- 1) IVIG treatment: Individuals with poorly controlled diabetes that have a sudden improvement in their HbA1C and the development of neuropathy (*meeting criteria for treatment induced neuropathy*). Subject number =10
- 2) Placebo Treatment: Individuals with poorly controlled diabetes that have a sudden improvement in their HbA1C and the development of neuropathy (*meeting criteria for treatment induced neuropathy*). Subject number =10.

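### The primary endpoint is a change in pain, but the SAP names no analysis model or baseline adjustment; adjusting for Visit 1 pain could gain power, by an amount that depends on a correlation the plan does not give

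*Combined protocol and SAP*

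**What the plan says.** The Primary endpoint section defines the outcome as "The change in neuropathic pain severity and distribution between treatment and placebo groups", measured from Visit 1 to Visit 2. It is a change from baseline compared between arms, and it covers both severity and distribution of pain.

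The Statistical Analysis Plan holds only power calculations. The pain calculation opens "We are planning a study of a continuous response variable from matched pairs of study subjects" and continues "If the true difference in the mean response of matched pairs is 3, we will need to study 10 pairs of subjects". Its table gives a change in pain score of 2 ± 2 on placebo and 5 ± 3 on IVIG. The section concludes that 10 per arm "will provide >80% power with a 2 sided alpha of 0.05 to detect a difference between placebo and active treatment groups". It names no primary test, regression model or covariate, and it gives no baseline SD, follow-up SD or correlation.

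Pain is recorded at the Screening Visit (Visit 1), where item 1 reads "Undergo a general physical examination, Pain VAS scores, pain questionnaires and SF-36". It is recorded again at Visit 4: "Undergo a general physical examination. Pain VAS scores, pain questionnaires and SF-36". Visits 2 and 3 list only the SF-36. The eligibility criteria set no range for baseline pain.

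**The concern.** A change score subtracts the whole baseline value. When baseline and follow-up are imperfectly correlated and similarly variable, that over-corrects: patients who start high tend to fall more whatever their arm. The change then carries baseline noise that a regression on baseline would remove. With 10 per arm, a chance imbalance in Visit 1 pain also moves the raw change comparison through regression to the mean.

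The protocol says the pilot is meant to estimate the size of the effect so that a larger trial can be powered, so avoidable noise in this estimate carries into the next sample size. The SAP's silence adds a second problem. If the model is not fixed in advance, adjusted or unadjusted analysis can be chosen after the results are seen.

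**Working it through.** **Inputs from the documents.** Difference in mean change 5 − 2 = 3; SDs of change 2 and 3 (reading ± as SD); two-sided alpha 0.05; 10 per arm, randomised equally, with no matching described; no dropout allowance stated, so none used.

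**Input not in the documents.** The correlation ρ between Visit 1 and follow-up pain. I take 0.3 to 0.7 as the working range and also show 0.8 and 0.9.

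**1. The plan's own figure.** Paired t-test, difference 3, SD of the pair difference 3, 10 pairs: noncentrality 3/(3/√10) = 3.162, df 9, power 80.3%. With 9 pairs it is 74.8%. The stated 10 pairs therefore reproduces.

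**2. The design described: two independent arms, unadjusted change.** Pooled SD = √((2² + 3²)/2) = 2.55. SE = 2.55 × √(2/10) = 1.140. Noncentrality 3/1.140 = 2.63, df 18, power 70.2% (Welch 69.4%). The 95% CI half-width is 2.101 × 1.140 = 2.40 points.

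**3. Adjusted for Visit 1 pain.** With equal baseline and follow-up variances and a common slope, residual SD = 2.55 × √((1 + ρ)/2). SE = residual SD × √(0.2 × (1 + 1/16)), where 1/16 allows for chance baseline imbalance; df 17, critical value 2.110.

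| Assumed ρ | Residual SD | SE | Power | Gain (points) | Half-width |
|---|---|---|---|---|---|
| 0.3 | 2.06 | 0.948 | 84.7% | +14.5 | 2.00 |
| 0.5 | 2.21 | 1.018 | 79.3% | +9.2 | 2.15 |
| 0.7 | 2.35 | 1.084 | 74.2% | +4.0 | 2.29 |
| 0.8 | 2.42 | 1.115 | 71.8% | +1.6 | 2.35 |
| 0.9 | 2.48 | 1.146 | 69.5% | −0.7 | 2.42 |

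Gains are taken before rounding. Simulation with 40,000 trials per setting agrees (84.8%, 79.5% and 74.2% at 0.3, 0.5 and 0.7).

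**4. Unequal SDs.** Simulating SDs of change of 2 and 3 with a common slope gives 84.4%, 79.5% and 74.5%, with type I error of 5.2% to 5.4%. The unequal spread alone does not remove the gain.

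**5. Slopes that differ by arm.** The Primary endpoint section expects percentage falls of more than 50% and less than 20%. Read as proportional effects (an assumption), these suggest follow-up-on-baseline slopes of about 0.5 on IVIG and 0.8 on placebo. With SDs of change of 3 and 2, unadjusted power is again about 70%. Adjusted power is 68%, 69%, 71%, 73% and 75% for baseline SDs of 1, 1.5, 2, 2.5 and 3, a gain of about −2 to +5 points. Mean half-width goes from 2.36 unadjusted to between 2.41 and 2.22. Much of the shortfall comes from the narrower baseline spread. At the average slope of 0.65, the model in step 3 implies a baseline SD of 2.55/√(2 × 0.35) = 3.05, and the gain near that spread is similar in both models.

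**The case against.** The strongest reply is that the plan contains no unadjusted analysis to criticise. It defines an endpoint and a sample size, and a change endpoint can be analysed with baseline as a covariate. That stands. A reader might infer that the SAP commits to a raw change comparison, or that it sized the trial as a simple difference of mean changes. It does neither: the model is unspecified and the sizing uses matched pairs. The 70% starting point is a recalculation for parallel arms.

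A reader might also infer a dependable gain of 4 to 14 points at no cost. The documents do not support that. No correlation is given, the gain shrinks to nothing as ρ approaches 0.9, and step 5 gives a weaker result. Wide baseline variation, which the open eligibility criteria allow, also points to the lower end: with the SD of change held at 2.55, step 3 implies a baseline SD of 2.15 at ρ = 0.3 and 3.29 at ρ = 0.7. Even at ρ = 0.7 the adjusted interval was narrower in only about 63% of simulated trials, so a single 20-patient study may see no benefit. Nor does a linear covariate cure the floor effect in patients who start with little pain.

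Finally, under randomisation an unadjusted change comparison is valid. The case for adjustment is one of efficiency, not of bias in the design.

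In the other direction, a large loss is unlikely. At ρ = 0.9 step 3 implies a baseline SD of 2.55/√0.2 = 5.7. If the VAS runs from 0 to 10 (the scale is not stated), an SD much above 5 is impossible.

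**Conclusion.** The point holds in a limited form. The primary endpoint is a between-arm comparison of change in pain, the SAP names neither a model nor a baseline adjustment, and the data for adjustment are already scheduled.

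Under equal variances and a common slope, adjusting for Visit 1 pain raises power from about 70% to between 74% and 85% for assumed correlations of 0.7 down to 0.3. Outside those assumptions the gain may be negligible or slightly negative.

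A reader might take adjustment as a way back to the stated power above 80%. In step 3 it falls just short at ρ = 0.5 and further short above that. The mismatch between matched pairs and parallel arms needs its own correction. The firmest reason to act is prespecification; the likely gain in precision supports it.

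**What to change.** First reconcile the endpoint visit. The Primary endpoint section names Visit 1 to Visit 2, but Visit 2 is the first treatment visit and lists only the SF-36. The next scheduled pain VAS after Visit 1 is at Visit 4. No adjusted model can be written until this is settled.

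Then add to the SAP:

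> The primary analysis estimates the between-arm difference in pain VAS at the reconciled post-treatment visit by linear regression on arm with Visit 1 pain VAS as covariate, reported as an adjusted difference with 95% CI. Pain distribution is analysed the same way with its own Visit 1 value where that is recorded. The unadjusted change-score comparison is a sensitivity analysis.

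For severity, this keeps the sponsor's change endpoint: regressing change instead of follow-up on arm and Visit 1 pain gives the same arm estimate and interval. The SAP should also name the measure of pain distribution, since the documents do not.

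Cost: a short SAP paragraph, one residual degree of freedom (17 instead of 18) and a variance penalty of about 1/16 for chance baseline imbalance. No new data or visits are needed for pain severity.

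### The arm-level pain changes in the power table do not agree with the percentage reductions expected under Primary endpoint; separately, the claim of more than 80% power rests on a matched-pairs formula, and two independent arms of 10 give about 70%

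*Combined protocol and SAP*

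**What the plan says.** Under Primary endpoint (combined protocol and SAP), the plan expects that IVIG subjects "will have a >50% reduction in neuropathic pain" 6 weeks after treatment, and "placebo that will have <20% reduction in neuropathic pain" at the same time. Both are one-sided limits in percent. No expected baseline pain score is given, and the range of the pain VAS is not stated.

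Under Power calculations in the Statistical Analysis Plan, the table gives the change in pain score as 2 (SD 2) for placebo and 5 (SD 3) for IVIG, in points, with no sign, scale or time point. The text uses the difference of these means: "If the true difference in the mean response of matched pairs is 3, we will need to study 10 pairs of subjects". It assumes that "the difference in the pain response of matched pairs is normally distributed with standard deviation 3", and adds: "The Type I error probability associated with this test of this null hypothesis is 0.05". The section then claims power above 80%, at a two-sided alpha of 0.05, for 10 subjects in each of two arms. The sources named are introduced by "Based on our preliminary data from the 4 subjects treated with IVIG, and the 104 untreated subjects with TIND".

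The opening Protocol text describes equal randomisation of 20 subjects to IVIG or placebo. It describes no matching of subjects.

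**The concern.** The plan describes the expected pain response twice, once in percent and once in points. The arms are randomised, so they share one expected baseline, and it should be possible to convert one description into the other. It is not: under the natural reading, the two tabulated falls cannot both satisfy the two percentages.

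The 3-point difference is the only effect assumption in the pain power calculation, and the SAP says the trial is powered for its primary endpoint. The results are also meant to power a larger trial. A reader comparing the observed effect with the planned one needs to know which expectation governs.

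The second issue arises at the same place but is distinct. The calculation is for matched pairs, while the design has two unmatched randomised arms, so the stated power is not that of the comparison described.

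**Working it through.** **Inputs.** Primary endpoint: IVIG reduction above 50%, placebo reduction below 20%. Power calculations: mean changes 5 (SD 3) and 2 (SD 2); paired difference 3 with SD 3; alpha 0.05, two-sided in the two-arm statement. Protocol: 10 per arm. The mean baseline B is not in the documents; it is varied here as an assumption.

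**Step 1: the plan's own figure.** Paired t-test, two-sided 0.05, noncentrality = (3/3) × √n. With n = 10 this is 3.16 and power is 0.803; with n = 9 it is 3.00 and power is 0.748. The stated 10 pairs is reproduced.

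**Step 2: points against percentages.** Read the changes as falls at 6 weeks and divide by a common mean B.

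- IVIG: 5/B > 0.50 requires B < 10.
- Placebo: 2/B < 0.20 requires B > 10.

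No B meets both. At B = 10 the falls are exactly 50% and 20%, on the limits.

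| B | IVIG, 5/B | Placebo, 2/B | Fails |
|---|---|---|---|
| 6 | 83% | 33% | placebo |
| 7 | 71% | 29% | placebo |
| 8 | 63% | 25% | placebo |
| 9 | 56% | 22% | placebo |
| 10 | 50% | 20% | both, at the limit |
| 12 | 42% | 17% | IVIG |

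**Step 3: what the percentages imply for the difference.** They require a difference above 0.50B − 0.20B = 0.30B. This is a floor, not an expected value: 2.1 points at B = 7, 2.4 at B = 8, 3.0 at B = 10. Differences of 3 or more fit comfortably:

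- B = 8 with 55% and 15%: 4.4 − 1.2 = 3.2.
- B = 7 with 60% and 15%: 4.2 − 1.05 = 3.15.

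If IVIG stays at 5 points and only the placebo fall is brought down to 20%, the difference rises: 5 − 1.4 = 3.6 at B = 7, and 5 − 1.6 = 3.4 at B = 8.

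**Step 4: power for two independent arms.** Two-sample t-test, 10 per arm, 18 degrees of freedom, two-sided 0.05, noncentrality = difference / (SD × √(2/10)). From the table, pooled SD = √((2² + 3²)/2) = √6.5 = 2.55.

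- Difference 3, SD 2.55: noncentrality 2.63, power 0.70.
- Difference 3, SD 3 in both arms: noncentrality 2.24, power 0.56.

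Reaching 80% at a difference of 3 would take 13 per arm with SD 2.55, or 17 with SD 3.

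**Step 5: sensitivity to the difference, 10 per arm.**

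| Difference | Power, SD 2.55 | Power, SD 3 |
|---|---|---|
| 2.1 | 41% | 32% |
| 2.4 | 51% | 40% |
| 2.7 | 61% | 48% |
| 3.0 | 70% | 56% |
| 3.4 | 81% | 67% |
| 3.6 | 85% | 72% |

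The shortfall at exactly 3 points is due to the change from paired to independent groups. The percentage mismatch plays no part in it.

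**The case against.** A reader might infer that the mismatch discredits the 3-point difference and so lowers the power. The documents do not support that. The percentages are open-ended, power depends on the difference and not on the two arm means separately, and 3 points is compatible with the percentages at ordinary baselines. Below a baseline of 10 the IVIG row already satisfies its limit, so correcting the placebo row alone makes the table's difference conservative. This objection stands in full. For the same reason, the powers at 0.30B must not be read as what the plan expects.

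The mismatch also depends on the reading. If percent reduction means the average of each subject's own percentage, it can disappear. As a constructed example, let half of each arm start at 4 and half at 10. Placebo falls of −0.2 and 4.2 average 2 points and 18.5%; IVIG falls of 2 and 8 average 5 points and 65%. The table does not say that its pain score is the VAS (pain questionnaires are also collected) or that it refers to 6 weeks. At a baseline of 10, reading the limits as approximate would remove the conflict, although on a 0–10 scale (an assumption) that would put the mean at the ceiling. These points make the conflict conditional. They do not remove the need to say which reading is meant.

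A reader might also infer that the placebo row is untreated-subject data, since the only sources named are 4 IVIG-treated and 104 untreated subjects. That is plausible, but the plan does not say which row came from which subjects, so it is not asserted here.

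**Conclusion.** Two things hold.

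First, the tabulated falls of 5 and 2 points do not agree with the expected reductions of more than 50% and less than 20%. This rests on three assumptions: the changes are falls, they refer to 6 weeks, and percentages are relative to a common mean baseline. The size depends on the unstated baseline; the placebo fall is 22% at 9 and 33% at 6, against a limit of 20%. It is an internal inconsistency in the arm-level assumptions. It neither excludes the 3-point difference nor shows a loss of power.

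Second, and independently, the claim of more than 80% power with 10 per arm does not hold for the design described. With the plan's own difference and SDs it is about 70%, and 56% if the paired SD of 3 is applied to each arm. That result assumes a two-sample t-test on change at two-sided 0.05 with all 20 subjects contributing.

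**What to change.** State the pain instrument and its range, and the expected mean baseline. Say whether percent reduction is the ratio of means or the mean of individual percentages. Express both arms' assumed changes on one basis, with direction and time point, so that the Primary endpoint section and the power table agree.

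Replace the matched-pairs justification and the claim of more than 80% power with the figure for two independent arms of 10: about 70% at a 3-point difference with SDs 2 and 3. Add a sensitivity range over the difference, such as the last table in the working.

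The cost is SAP wording, a short recalculation and a less favourable stated power. No more patients are needed if the trial is presented as a pilot with that power.

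### Read literally, the secondary outcomes compare follow-up scores with no baseline term while the stated expectations concern change; ignoring the Visit 1 values costs precision but does not cause bias

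*Combined protocol and SAP*

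**What the plan says.** The Secondary Outcomes section names the comparison as "The difference in quantified neurologic examination scores, biopsy scores and autonomic function between treatment and placebo groups at 6 weeks and 12 weeks". That sentence contrasts the arms and mentions neither change nor baseline.

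The paragraph below it gives expectations in other terms. The IVIG arm is expected to show "improvements in quantified neurologic examination scores, autonomic function testing and nerve fiber density". Both arms are described by "nerve fiber density at follow up visits 4 and 5 compared to their initial visit".

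Two other places also speak of change. The primary endpoint is "The change in neuropathic pain severity and distribution between treatment and placebo groups between visit 1 and visit 2". The table under Power calculations in the Statistical Analysis Plan has a column headed "Change in IENFD" (placebo 0.5, SD 1; IVIG 3, SD 1.9). UENS and autonomic function are not in that table, and the SAP says that secondary endpoints are outside the power analysis.

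The SAP consists of power calculations and group sizes. It names no model, covariate, change-score rule or stratification. UENS, heart rate variability and the distal leg biopsy are all scheduled at Visit 1 and again at Visit 4.

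**The concern.** The outcome sentence and the expectation paragraph do not describe the same quantity: one is a difference between arms in follow-up level, the other a change from the first visit. With no model in the SAP, an analyst could defend a comparison of follow-up scores, of change scores, or of baseline-adjusted scores, and could choose after seeing the data.

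The literal version leaves out a measurement that the trial already takes. With 10 patients per arm, chance differences at Visit 1 are not small, and part of them carries into a follow-up comparison as noise. The protocol's aim is to estimate the size of the treatment effect, including on neuropathy severity, in order to power a larger trial. Avoidable noise in that estimate weakens what the pilot is meant to deliver.

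**Working it through.** **Plan's own figures.** A two-sided paired t-test at alpha 0.05 (noncentral t) reproduces both stated sizes.
- Pain: difference 3, SD 3, n = 10 pairs gives power 80.3%. The SAP says "If the true difference in the mean response of matched pairs is 3, we will need to study 10 pairs of subjects".
- IENFD: difference 2.5, SD 1.9, n = 7 pairs gives power 82.5%. The SAP says "If the true difference in the mean response of matched pairs is 2.5, we will need to study 7 pairs of subjects".

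These are paired calculations for a trial with two parallel arms. That is a separate matter and is not needed here.

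**Inputs.** From the documents: 10 per arm, 20 in total, equal randomisation, no stratification stated. Assumed, because the documents give neither a correlation nor a cross-sectional SD: equal variance at the two visits, and rho of 0.3, 0.5, 0.7 or 0.8.

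**Step 1: chance baseline difference.** In units of the between-patient SD, the SD of the difference in means is sqrt(2/10) = 0.447. The chance that it exceeds 0.5 SD in either direction is P(|Z| > 0.5/0.447) = P(|Z| > 1.118) = 0.26.

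**Step 2: the part that reaches the result.** A follow-up comparison carries rho times the baseline difference, so the carried part has SD rho × 0.447.

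**Step 3: variance relative to a follow-up-only comparison.** A simple change score gives 2(1 − rho). ANCOVA gives 1 − rho², multiplied by 1 + 1/(20 − 4) = 1.0625 for estimating the slope.

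| rho | carried part, SD | change score | ANCOVA before slope cost | ANCOVA after slope cost |
|---|---|---|---|---|
| 0.3 | 0.13 | 1.40 | 0.91 | 0.97 |
| 0.5 | 0.22 | 1.00 | 0.75 | 0.80 |
| 0.7 | 0.31 | 0.60 | 0.51 | 0.54 |
| 0.8 | 0.36 | 0.40 | 0.36 | 0.38 |

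A change score is worse than the follow-up score alone when rho is below 0.5, so simply inserting the word change would not be a full repair.

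**Step 4: IENFD on the plan's scale.** The pooled change SD is sqrt((1² + 1.9²)/2) = 1.52. Under the equal-variance assumption the cross-sectional SD is 1.52/sqrt(2(1 − rho)). Power is for a difference of 2.5 with 10 per arm, two-sided alpha 0.05.

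| rho | cross-sectional SD | carried part, SD | power, follow-up only | power, ANCOVA |
|---|---|---|---|---|
| 0.3 | 1.28 | 0.17 | 98% | 99% |
| 0.5 | 1.52 | 0.34 | 94% | 97% |
| 0.7 | 1.96 | 0.61 | 77% | 95% |
| 0.8 | 2.40 | 0.86 | 60% | 94% |

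The change-score comparison has 93.6% power at every rho, because its SD is fixed by the table. No such calculation is possible for UENS or autonomic function, for which the documents give no figures.

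**The case against.** The strongest reply is that the plan never says it will ignore baseline. A reader might infer that a follow-up-only analysis has been chosen, but that is only the literal sense of one sentence. The expectation paragraph, the primary endpoint and the IENFD column all point to change, so a between-arm difference in change may have been intended. This stands. What the documents show is an outcome whose wording and expectation differ, with no model to settle which applies.

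A reader might also infer that each arm is to be tested against its own first visit, giving up the randomised comparison. The documents do not say so: those sentences are expectations, and the outcome sentence is explicitly between groups. Nor does the power table show that all the secondary outcomes were sized on change. It covers IENFD alone, and it does not state the visit from which change is measured.

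On size, the 26% describes imbalance at baseline and not error in the result. The chance that the carried part exceeds 0.5 SD is P(|Z| > 0.5/(rho × 0.447)): about 2.5% at rho 0.5, 11% at 0.7 and 16% at 0.8. This stands too, as does the point that these are secondary outcomes in a 20-patient pilot. None of it supplies the missing model or makes use of the Visit 1 values.

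**Conclusion.** The point holds as an unresolved wording conflict and a loss of efficiency. It is worth correcting, but it is not an error in the plan's arithmetic.

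A reader might conclude that chance imbalance would bias the secondary results or inflate false positives. That does not follow. Under randomisation the imbalance is random error, the unconditional type I error stays at 5%, and an ordinary confidence interval already allows for it. The cost is a wider interval than the data require.

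The size depends on rho, which is assumed. The gain from adjustment is negligible at 0.3 (variance 97% of follow-up-only), modest at 0.5 (80%) and material at 0.7 and above (54%, and 38% at 0.8). The results in SD units assume equal variance at the two visits. The IENFD power figures also rest on the table's two SDs pooled to 1.52.

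**What to change.** In the SAP, define each secondary outcome (UENS, IENFD, heart rate variability) as the between-arm difference in the Visit 4 score, estimated by ANCOVA with arm and the patient's own Visit 1 score as terms. Report the adjusted difference with its 95% CI as the effect estimate for planning the larger trial. Present within-arm change as description only. It would also help to report the observed correlation between Visit 1 and Visit 4, since the documents contain no value for it.

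For Visit 4 the cost is a change of SAP wording and one degree of freedom per model (18 to 17 residual with 20 patients). No extra measurement is needed.

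The 12-week part cannot be settled by wording the model alone. The outcomes refer to 12 weeks and Visit 5, but the visit schedule ends at Visit 4, 28 ± 3 days after the second treatment. The sponsor should reconcile these, and state which visit the 6-week label denotes, before applying the same model at a later time point.
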